Early Treatment of Cytokine Storm Syndrome in Covid-19

NCT04362111

UAB IRB Final Approval Date: July 28 2020

Protocol

Introduction

Macrophage Activation Syndrome (MAS) or Cytokine Storm Syndrome (CSS) is a disorder consisting of massive systemic inflammation, multi-organ system failure, disseminated intravascular coagulopathy, and often severe morbidity/mortality. Reports from areas initially impacted by Covid-19 confirm clinical and laboratory features present in patients with respiratory failure that are identical to those associated with Cytokine Storm Syndrome (CSS) occurring in the setting of other disorders and viral infections (1,2). The recombinant human IL-1 soluble receptor antagonist (rhIL-1ra) anakinra has a short half-life of 4-6 hours, is quick acting and in multiple case reports/series has been reported to be safe as well as effective in treating CSS occurring in the setting of herpes virus infections (EBV/CMV/HSV), ehrlichiosis, sepsis syndromes, adult Still disease/systemic JIA, and systemic lupus (3-6). In children with severe flares of sJIA, doses as high as 100 mg sc every 6 hours have been employed with success (7) and in the absence of significant noted toxicities. In previous trials of anakinra use for management of sepsis, doses up to 3500 mg/day were employed over 72 hours without any noted serious toxicities attributed to anakinra (8). In a recent study examining outcomes in the phase III sepsis trials, treatment with anakinra was associated with improved survival in a subgroup with MAS attributes including hepatic dysfunction and coagulopathy (4) Trials of anakinra to treat CSS in hospitalized patients with Covid-19 infection and features of CSS are therefore warranted.

Specific Aims

The specific aims of the trial are to determine whether treatment with anakinra added to standard of care treatment for hospitalized patients with Covid-19 pneumonia results in:

1. . Survival and discharge from the hospital without the need for intubation/mechanical ventilation. (Primary outcome)
 1. No increase in oxygen requirement or oxygen delivery measures to maintain $\text{SaO}_2 > 90\%$ at 48 hours compared to baseline at study entry/randomization. (Primary outcome)
 2. No increase in oxygen requirement or oxygen delivery measures to maintain oxygen saturation $>90\%$ Day 2 (48 hours) through Day 105 (120 hours). (Secondary outcome)
 3. At least 25% decrease in serum ferritin, LDH, CRP, and d-dimer at 48 hours. (Secondary outcome)

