 4. Normalization by Day 5 of laboratory CSS attributes: ferritin, fibrinogen, AST, ALT, leucopenia, tryglycerides, sCD25 (Secondary outcome)
 5. Normalization or $\geq 75\%$ improvement by Day 10 (120 hours) in each of the following laboratory CSS attributes elevated beyond the normal range at randomization: ferritin, fibrinogen, AST, ALT, leucopenia, thrombocytopenia, d-dimer, CRP, triglycerides, sCD25. (Secondary outcome)
 6. Decreased time to achievement of $\geq 93\%$ oxygen saturation on room air. (Secondary outcome)
 7. No increased prevalence of nosocomial bacterial or fungal or viral infection through the time of hospital discharge. (Secondary outcome)
 8. No failure to develop neutralizing antibody to Covid-19 measured at Day 28. (Secondary outcome)
5. Discharge from hospital without the need for intubation/mechanical ventilation. (Secondary outcome)

Significance

If shown effective, early identification of CSS and repurposing anakinra for its treatment in severe Covid-19 illness will help reduce ICU admissions, improve patient outcomes and enhance survival.

Confirmation of a genetic basis for susceptibility to Covid-19 associated CSS as we identified in H1N1 associated deaths (6) will also facilitate risk stratification and future targeted approaches to Covid-19 disease management.

Design

Recruitment and Enrollment: Thirty patients will be recruited for enrollment; potential subjects will be identified from the registry of Covid-19 patients admitted to the University of Alabama Hospital.

Patient Compensation: Not applicable

Eligibility/Inclusion Criteria:

Inclusion criteria:

1. 18 years old or older
2. Molecular diagnosis of SARS-CoV-2 infection and Covid-19 pneumonia
3. Radiographic imaging consistent with Covid-19 pneumonia
4. Room air oxygen saturation <93%
5. Hyperferritinemia (>700 ng/ml)
6. Any three of the following:
 - a. elevated d-dimer (> 500 ng/ml)
 - b. thrombocytopenia (< 130,000/mm³)
 - c. leucopenia (WBC < 3500/mm³) or lymphopenia (<1000/mm³)
 - d. elevated AST or ALT (> 2X ULN)
 - e. elevated LDH (> 2X ULN)
 - f. CRP > 100 mg/L

Exclusion criteria:

1. Participation in other investigational treatment protocols for Covid-19 infection
2. Culture confirmed active bacterial infection requiring antibiotic therapy
3. On mechanical ventilation
4. Previous known hypersensitivity reaction to anakinra
5. Previous known hypersensitivity reaction to E Coli derived proteins
6. Pregnant or breast-feeding females

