Subjects in the SoC only arm with deterioration of respiratory parameters and CSS markers at 48-96 hours will be transitioned to treatment with anakinra. Patients will stay on anakinra until all CSS markers no longer exceed the thresholds required for enrollment or through Day 5 of anakinra treatment, whichever comes first. Anakinra may be continued after Day 5 of treatment at the discretion of the treating physicians.

Informed Consent:

Identified patients who may be eligible for enrollment will be asked to consider participation in the protocol in the context of the informed consent process whereby the risks and benefits of their participation are discussed with a study investigator. As subjects with CSS/MAS are often severely ill,

those with any suspected altered sensorium will not be enrolled without the assent of a family member who is the designated representative of the patient to assist with their decision whether or not to participate.

Randomization:

Randomization will be assigned by the study coordinator using a computer-based randomization algorithm. The respective PIs will remain blinded to treatment group assignment for all subjects until study completion.

Visit Schedule and Study Procedures

Following obtaining informed consent and 1:1 randomization by computer, study assessments will be as follows:

Day 0:

- Record vital signs, ventilation and oxygen support, heart function, and kidney function/support.
- Blood drawn for these tests:
 - ferritin, CBC with diff, CMP, ESR, CRP, fibrinogen, D-dimer, INR/PT, LDH triglyceride level
 - Cytokine-12 panel, IL-18, CXCL9, sCD25, sCD163, IL-1 β , NK/B/T-cell lymphocytes
 - NK cell function assay
- Blood sample for genetic testing for perforin pathway (genetic traits associated with CSS)

Every effort will be made to procure remdesivir as available under existing PUA for all enrolled subjects.

Following completion of the baseline assessments, dosing of study agent (100 mg anakinra or equal volume saline placebo) will commence every 6 hours by subcutaneous administration.

Day 1-Day 9:

- Record vital signs, ventilation and oxygen support, heart function, and kidney function/support.
- Blood drawn for these tests: ferritin, CBC with diff, CMP, ESR, CRP, fibrinogen, D-dimer, INR/PT, LDH

Day 10:

- Record vital signs, ventilation and oxygen support, heart function, and kidney function/support.
- Blood drawn for these tests:

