The primary efficacy analysis will be conducted on a modified intention-to-treat basis and defined as all patients who underwent randomization and received either anakinra or placebo before intubation/mechanical ventilation or death. Descriptive statistics will be used to characterize participants. Continuous data will be summarized by means and standard deviation (SD) and analyzed by student t tests. Categorical data will be described with frequencies and percentages and compared using Fisher's exact or chi square tests. Cox proportional hazards models will be used to calculate hazard ratio for the association between treatment group and death from any cause or need for mechanical ventilation; due to small sample size control for demographic characteristics, clinical variables and comorbidities will likely not be possible. Calculated 95% confidence interval (CI) and $p < 0.05$ will be considered significant. All analysis will be conducted with SAS v 9.4 (Cary, NC, USA).

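### With about 15 patients per arm, the Cox analysis names no test or interval type and has no provision for an arm with few or no events

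*Combined protocol and SAP*

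**What the plan says.** The Statistical Analysis Plan sets the time-to-event analysis: "Cox proportional hazards models will be used to calculate hazard ratio for the association between treatment group". The event in that model is a composite, given as "death from any cause or need for mechanical ventilation". The criterion follows: "Calculated 95% confidence interval (CI) and $p < 0.05$ will be considered significant". It does not say whether the interval and p-value are Wald, likelihood-ratio, score or another kind.

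Sample size and allocation come from the Design section ("Thirty patients will be recruited for enrollment") and from Visit Schedule and Study Procedures ("Following obtaining informed consent and 1:1 randomization by computer"). Together they imply about 15 patients per arm. The modified intention-to-treat rule could make the arms slightly smaller.

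The only allowance for small numbers concerns covariates: "due to small sample size control for demographic characteristics, clinical variables and comorbidities will likely not be possible". Nothing is said about the treatment coefficient when events are few.

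The same section also plans a test that copes with a zero cell: "Categorical data will be described with frequencies and percentages and compared using Fisher's exact or chi square tests". The first primary outcome in Specific Aims is binary in form, so this sentence can apply to it. The plan does not say whether that test or the Cox model decides.

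**The concern.** A Cox model with treatment as its only covariate needs events in both arms to give a finite log hazard ratio. If one arm has none, the partial likelihood keeps rising as the coefficient moves away from zero. The program then stops at an arbitrary large value with an enormous standard error. The hazard ratio that the plan promises cannot be reported, and a Wald interval or p-value is meaningless.

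If treatment works well, an empty anakinra arm becomes more probable, so the difficulty is greatest where the effect is largest. With one or two events the estimate exists, but which test is read from the output can decide whether p falls below 0.05. Since the plan names no test, that choice could be made after the data are seen.

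**Working it through.** **Inputs.** From the documents: 30 patients, 1:1, so 30/2 = 15 per arm; significance at 0.05, taken as two-sided to match a 95% interval. Event rates and event timing are not in the documents and are assumptions below. The plan states no power, effect size or event count, so there is no figure of its own to reproduce.

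**1. Chance of an empty arm.** P(0 events in 15) = (1 − risk)^15.

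| Assumed risk in that arm | Calculation | P(zero events) |
|---|---|---|
| 5% | 0.95^15 | 46% |
| 10% | 0.90^15 | 21% |
| 15% | 0.85^15 | 9% |
| 20% | 0.80^15 | 3.5% |
| 30% | 0.70^15 | 0.5% |

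The chance of at most two events is 82% at 10% risk, 40% at 20% and 13% at 30%.

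**2. What the model gives at 0/15 v 6/15** (no censoring before the last event). At the six events the anakinra risk set stays at 15 and the control risk set is 15, 14, 13, 12, 11, 10.
- Log partial likelihood: −Σ log(15·e^b + r₀). It rises steadily as b goes to minus infinity, so there is no finite maximum. Numerically the hazard ratio is about 1e-8, the standard error is in the thousands and Wald p is about 0.99. The same p appears even at 0/15 v 15/15.
- Likelihood ratio: 2·Σ log[(15 + r₀)/r₀] = 2 × 4.776 = 9.55, p=0.002.
- Score (log-rank): with pᵢ = 15/(15 + r₀), (Σpᵢ)²/Σpᵢ(1 − pᵢ) = 3.285²/1.479 = 7.30, p=0.007.
- Fisher's exact: 2 × C(15,6)/C(30,6) = 2 × 5005/593775 = 0.017.
- Firth's penalised likelihood: hazard ratio 0.06, profile-likelihood 95% CI 0.0005 to 0.53, p=0.007.

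**3. One or two events in the anakinra arm** (illustrative event times).

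| Events | HR (Wald 95% CI) | Wald p | LR p | Fisher p |
|---|---|---|---|---|
| 1 v 6 | 0.14 (0.017 to 1.19) | 0.073 | 0.030 | 0.080 |
| 1 v 7 | 0.12 (0.015 to 0.96) | 0.046 | 0.013 | 0.035 |
| 2 v 8 | 0.20 (0.04 to 0.93) | 0.041 | 0.021 | 0.050 |

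All estimates are finite. Wald p is larger than LR p in each row, and at 1 v 6 the choice of test decides significance.

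**4. Power if the Wald test were used.** Simulation of 15 per arm, exponential event times with mean 4 days, and event-free patients followed to Day 60. With 3,000 to 4,000 trials per scenario the Monte Carlo standard error is at most √(0.5 × 0.5/3000) = 0.9 percentage points.

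| Risk, anakinra v control | Wald | Log-rank | Firth |
|---|---|---|---|
| 10% v 40% | about 20% | 49% | 48% |
| 20% v 50% | 29% | 40% | not run |
| 30% v 60% | 33% | 39% | not run |
| 20% v 20% (no effect) | 0.6% | 5.1% | 5.0% |

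Fisher's exact reached 32% at 10% v 40%. With no effect at 40% v 40% the Wald error rate was 3.4%, so its conservatism fades as events accumulate.

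**5. Why not plain likelihood ratio.** In a second simulation (28-day horizon) with no effect and a 10% event rate, the unpenalised likelihood-ratio test rejected in 8% of trials, against a nominal 5%.

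**The case against.** A reader might infer that the strongest possible benefit would be reported as non-significant. The documents do not support that. The plan never names the Wald test, and the likelihood-ratio and score tests from the same model are clearly significant at 0 v 6. Fisher's exact test is already planned and reaches p=0.042 at 0 v 5 and p=0.017 at 0 v 6.

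A reader might also infer that an empty arm is likely. No event rate is given. Eligibility requires room-air saturation below 93%, ferritin above 700 ng/ml and three further abnormalities, so a low risk cannot be presumed. At 30% risk or more the chance of an empty arm is below 1%.

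Nor does the model break down with one or two events. The estimates are finite, and at 2 v 8 the Wald p (0.041) is slightly smaller than Fisher's (0.050).

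Finally, Firth's method is one remedy among several, since log-rank performs as well as a test.

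These points remove any claim that the plan will miss a benefit. They leave three things standing. No choice of test gives a finite ordinary hazard ratio when an arm is empty, and the hazard ratio is what the plan promises. Fisher's exact supplies no hazard ratio, has less power than log-rank or Firth (32% against 49% and 48% at 10% v 40%), and is not stated to be decisive. Log-rank alone supplies no estimate, and an unpenalised profile likelihood gives a finite upper limit (0.31 at 0 v 6) but no point estimate.

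**Conclusion.** The concern holds in conditional form. As written, the Cox analysis cannot deliver its hazard ratio if one arm has no events, and it leaves the test and interval open where that choice can decide significance. How often this arises depends on risks that the documents do not give: the chance of an empty arm of 15 runs from 46% at 5% risk to 0.5% at 30%. The loss of power applies only if the Wald test is the one used. It is then large at 10% v 40% risk (about 20% against 49% for log-rank) and modest at 30% v 60% (33% against 39%). These figures assume 15 analysed per arm, exponential event times and follow-up to Day 60. The plan should be changed, but nothing here shows that a real effect would go undetected.

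**What to change.** In the Statistical Analysis Plan:

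- Fit the Cox model with Firth's penalised likelihood and report the hazard ratio with a profile-likelihood 95% confidence interval, whatever the event counts.
- Take the Cox p-value from one named test, the penalised likelihood-ratio test, so that it agrees with that interval. Do not use the Wald test.
- State whether this test or Fisher's exact test is decisive.

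The cost is a sentence or two and a software option in the SAS release that the plan already names. Patients, data collection and sample size are unaffected. The drawback is slight shrinkage of the hazard ratio. The method also does not turn very thin data into a positive result: at 0 v 3 events it gives p=0.097.

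### Eight secondary outcomes, up to 26 tests if each laboratory marker is tested, share one per-test p < 0.05 rule with no order, gate, adjustment or exploratory label

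*Combined protocol and SAP*

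**What the plan says.** The Specific Aims section opens with confirmatory language, "The specific aims of the trial are to determine whether treatment with anakinra added to standard of care treatment", and then lists the outcomes. Two are labelled primary and eight secondary: the nested items 2 to 8, and the closing item on discharge without ventilation.

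Three of the eight secondary outcomes are marker lists:
- 48 hours, four markers: "At least 25% decrease in serum ferritin, LDH, CRP, and d-dimer at 48 hours. (Secondary outcome".
- Day 5, seven markers: "Normalization by Day 5 of laboratory CSS attributes: ferritin, fibrinogen, AST, ALT, leucopenia", followed by triglycerides and sCD25.
- Day 10, ten markers, with the criterion of normalization or "improvement by Day 10 (120 hours) in each of the following laboratory CSS attributes elevated beyond the normal range at randomization".

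The Statistical Analysis Plan is one paragraph that does not name the secondary outcomes. It assigns tests by data type: "Continuous data will be summarized by means and standard deviation (SD) and analyzed by student t tests" and "Categorical data will be described with frequencies and percentages and compared using Fisher's exact or chi square tests". The only decision rule is "Calculated 95% confidence interval (CI) and $p < 0.05$ will be considered significant". The document gives no testing order, no condition on the primary result, no split or adjustment of alpha, no rule for combining markers, and no statement that secondary results are exploratory.

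**The concern.** The Design section plans 30 patients, so the primary comparison may well be inconclusive. The easiest positive statement would then be one marker at one time point with p < 0.05. The plan allows that to be called significant, and nothing in it tells a reader how many such chances there were. At stake is what the trial may claim about cytokine storm markers: a result of the kind that chance often produces could be reported in the same terms as a successful primary outcome.

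**Working it through.** **Inputs from the document.** Threshold 0.05 per test; Student t, and Fisher's exact or chi-square with the choice left open (Statistical Analysis Plan). N = 30 (Design), randomized 1:1 (Visit Schedule and Study Procedures), so 30/2 = 15 per arm. Sidedness is not stated; two-sided is assumed because p < 0.05 is paired with a 95% interval. The plan gives no family-wise error rate, so there is no plan figure to reproduce.

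**Count of tests.**
- Outcome level: 8.
- Marker level: 4 + 7 + 10 = 21 markers, plus the 5 other outcomes = 26.
- Against the visit schedule: triglycerides and sCD25 are drawn on Day 0 and Day 10 but are not among the Day 1–9 tests, so two of the seven Day 5 markers have no scheduled draw: 26 − 2 = 24. The Day 28 antibody outcome has no listed draw either, since the listed visits end at Day 10: 24 − 1 = 23. So 26 is an upper bound, and the schedule supports 23 or 24.

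**Simple bound.** For m independent tests with true size 0.05, the chance of at least one false positive is 1 − 0.95^m:
- m = 8: 1 − 0.95^8 = 33.7%
- m = 26: 1 − 0.95^26 = 73.6%

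This overstates the risk, because the outcomes are correlated and Fisher's test is conservative at 15 per arm.

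**Actual test size at 15 per arm (exact calculation, independent tests).**

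| Response rate | Fisher size | 8 Fisher tests | Chi-square size | 8 chi-square tests |
|---|---|---|---|---|
| 10% | 0.55% | 4.3% | 2.5% | 18.1% |
| 30% | 1.7% | 12.8% | 5.5% | 36.3% |
| 50% | 1.65% | 12.5% | 4.6% | 31.2% |

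**Simulation with correlation.** No treatment effect and 15 per arm; equicorrelated latent normal variables are cut to give response rates of 30% or 50%. The time-to-saturation outcome is tested by t test and all others as binary. The rates and the correlation of 0.5 are assumptions, since the document gives neither. Chance of at least one p < 0.05 in either direction:

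| Family | Fisher | Uncorrected chi-square |
|---|---|---|
| 8 outcome-level tests | about 13% | about 27–30% |
| 23–26 marker-level tests | about 26–30% | about 51–64% |

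Repeated runs differ by a point or two.

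**Sensitivity.**
- Correlation from 0 to 0.8: eight tests run from 11% to 16% (Fisher) and 20% to 36% (chi-square); 26 tests run from 18% to 38% and from 37% to 77%.
- Direction: counting only errors that favour anakinra roughly halves the figures, so about 13% becomes about 6–7%.
- Response rates of 10%: eight tests with Fisher give about 4–9%. The low end treats all eight as binary; the higher values keep the one t test.

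**The case against.** The strongest reply is that the outcomes are already labelled primary and secondary, in a 30-patient trial whose plan concedes that its sample is small, and that readers discount secondary p-values anyway. The significance sentence also follows the Cox model, in a paragraph that opens with the primary efficacy analysis, so it might be meant for that analysis alone. The labels do help, but the only rule written down attaches the word significant to p < 0.05 without restriction, and t tests for continuous data fit neither primary outcome. If the sentence was meant for the primary analysis only, saying so is the same correction.

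Several points on size do stand:
- A reader might take 26 as the number of planned tests. Only the Day 10 outcome is worded marker by marker; the 48-hour and Day 5 lists could be composites, and three of the 26 tests have no scheduled draw.
- A reader might quote the chi-square figures alone. At 15 per arm and 30% response the expected count is 15 × 0.30 = 4.5, where Fisher's test, which the plan names first, is the usual choice. The plan nevertheless leaves the choice open.
- The figures count errors in both directions. Two of the eight outcomes (infection and antibody) are framed as absence of harm, so a significant difference there could be a safety signal, not a claim of benefit. The discharge outcome nearly duplicates the first primary.
- The Day 10 outcome covers only markers abnormal at randomization, so some tests will have fewer than 15 per arm and Fisher's test will be more conservative still.

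**Conclusion.** The gap is real: nothing in the plan governs which secondary results may be called significant. On the stated assumptions (no effect, 15 per arm, response rates 30–50%, correlation 0.5), the chance of at least one nominally significant secondary result lies between about 13% and 30% at outcome level, and between about 26% and 64% if markers are tested singly. Much of each range comes from the open choice between Fisher and chi-square. Errors in anakinra's favour are roughly half as likely.

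A reader might go further and say that the error rate is many times the 5% the plan promises. The document does not support that. Its 0.05 is a threshold for each test and it states no family-wise rate, so such a ratio compares two different quantities. Nor is inflation above 5% certain in every case: eight Fisher tests at 10% response rates give about 4–9%. The case for a change rests on the missing rule, not on any one multiplier.

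**What to change.** Limit the p < 0.05 sentence in the Statistical Analysis Plan to the primary analysis, and add wording such as:

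> *All secondary outcomes, including each laboratory marker and each time point, are exploratory. They will be reported as between-arm estimates with 95% confidence intervals and nominal p-values, without a claim of significance. The number of comparisons made will be stated.*

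A key secondary outcome tested only after primary success is not recommended here: the plan has two primary outcomes and no rule for what counts as primary success, so the gate would be undefined.

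The cost is two or three sentences of text, with no new patients, data or procedures. The one small loss is that a lone secondary p < 0.05 could no longer be called a significant effect.
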